9.4.2.5. Hepatic Injury

For **Grade 2** immune-mediated hepatitis, liver function tests must be monitored more frequently until returned to baseline values (consider weekly). Treatment with I.V. or oral corticosteroids shall be considered.

For **Grade 3-4** immune-mediated hepatitis, intravenous corticosteroids are recommended for 24 to 48 hours.

When symptoms improve to Grade 1 or less, a steroid taper should be started and continued over no less than 4 weeks.

If a patient experiences elevated ALT $>3 \times$ ULN and/or elevated total bilirubin $>2 \times$ ULN, clinical and laboratory monitoring may be initiated, at the discretion of the investigator. For patients with liver metastasis who begin treatment with Grade 2 AST or ALT, if AST or ALT increases by greater than or equal to 50% relative to baseline and lasts for at least 1 week, then patients should be discontinued.

Details for hepatic monitoring depend upon the severity and persistence of observed laboratory test abnormalities. To ensure patient safety and comply with regulatory guidance, the investigator is to consult with the Lilly CRP regarding collection of specific recommended clinical information and follow-up laboratory tests. See Site Guidance Document for Drug-Induced Liver Injury (DILI).

9.4.2.6. Renal Failure or Immune-Mediated Nephritis

In case of **Grade 2** events, treatment with corticosteroids is recommended.

Patients that experience **Grade 3-4** events shall be treated with systemic corticosteroids.

When symptoms improve to Grade 1 or less, steroid taper should be started and continued over no less than 4 weeks.

Pembrolizumab must be withheld for moderate (Grade 2) nephritis, and permanently discontinued for severe (Grade 3) or life-threatening (Grade 4) nephritis.

9.5. Blinding

This is an open-label study.

9.6. Concomitant Therapy

Appropriate documentation of all forms of premedications, supportive care, and concomitant medications must be captured at each visit in the CRF. Concomitant medications and supportive care therapies must also be documented at the time of discontinuation and at the 30-day short-term follow-up visit.

With the exceptions listed in the sections below, no other chemotherapy, experimental medications, other anticancer therapy or biological therapy, immunotherapy not specified in this protocol, hormonal cancer therapy, radiation, surgery for cancer, or experimental medications will be permitted while patients are on study treatment.

Palliative radiotherapy, unless required due to PD, is permitted during the study.

- Radiation therapy to a symptomatic solitary lesion or to the brain may be considered on an exceptional case-by-case basis after consultation with the sponsor. The patient must have clear measurable disease outside the radiated field. Administration of palliative radiation therapy will be considered clinical progression for the purposes of determining PFS.

Live vaccines within 30 days prior to the first dose of trial treatment and while participating in the trial are not allowed. Examples of live vaccines include, but are not limited to, the following: measles, mumps, rubella, chicken pox, yellow fever, rabies, BCG, and typhoid (oral) vaccine. Seasonal influenza vaccines for injection are generally killed-virus vaccines and are allowed. However, intranasal influenza vaccines (for example, Flu - Mist®) are live attenuated vaccines and are not allowed.

Systemic glucocorticoids for any purpose other than to modulate symptoms from an AE of suspected immunologic etiology are not permitted. The use of physiologic doses of corticosteroids may be approved after consultation with the sponsor. Inhaled steroids are allowed for management of asthma; similarly, intranasal steroids for rhinitis and/or sinusitis are allowed.

Patients who, in the assessment by the investigator, require the use of any of the aforementioned treatments for clinical management should be removed from the trial. Patients may receive other medications that the investigator deems to be medically necessary.

The exclusion criteria describe other medications that are prohibited in this trial.

There are no prohibited therapies during the Post-Treatment Follow-up Phase.

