
Criteria for Evaluation: Efficacy: Objective Response Rate (ORR) is defined as the proportion of patients achieving a best overall response of partial response (PR) or complete response (CR). Disease Control Rate (DCR) is defined as the proportion of patients achieving a best overall response of stable disease (SD), PR, or CR. Progression-Free Survival (PFS) is defined as the time from the date of first dose of any study drug until the date of radiographically documented PD or death due to any cause, whichever is earlier. Overall Survival (OS) is defined as the time from the date of first dose of any study drug to the date of death from any cause. Safety: Part A and Part C: DLTs, serious adverse events (SAEs), adverse events (AEs), vital sign measurements, laboratory analyses, and electrocardiograms (ECGs) Part B: SAEs, AEs, vital sign measurements, laboratory analyses, and ECGs Pharmacokinetics: Serum concentrations of necitumumab prior to infusion (minimum concentration [C_{min}]) and at end of the necitumumab infusion (approximately maximum concentrations for necitumumab). Bioanalytical: Serum concentrations of necitumumab will be measured using validated enzyme-linked immunosorbent assays. Immunogenicity: Serum anti-necitumumab antibody titer levels will be determined. Translational research: A tumor tissue block or tumor tissue slides will be collected to correlate biomarker results with clinical outcomes related to the EGFR pathway, innate and adaptive immunity, and/or other biomarkers associated with the disease pathobiology and therapeutic molecules. Blood samples will be collected for exploratory biomarker analyses.

Statistical Methods:

Efficacy: The primary Part B outcome variable in this study will be the ORR. The Part B statistical null hypothesis states that the true ORR is 20%, whereas the research hypothesis states that the true ORR is 35%. If the research hypothesis is true, there is an 83% chance of rejecting the null hypothesis. If the null hypothesis is true, then there is at most a 10% chance of rejecting the null hypothesis. Therefore, the sample size of 54 evaluable patients in Part B has a nominal one-sided alpha level of 0.10, with statistical power of 83%.

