12.2. Statistical and Analytical Plans

12.2.1. General Considerations

The primary analysis will be as described in Section 12.1.

All efficacy summary analyses will be performed for all evaluable patients (as defined in Section 12.1). All safety summary analyses will be performed for all treated patients (those enrolled in the study who receive any amount of study drug [necitumumab and/or pembrolizumab]).

Minor changes or clarifications to any statistical analyses described in this protocol may be presented in the final statistical analysis plan (SAP) for this study.

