12.2.7. Analyses of Efficacy

In addition to the analyses described in Section 12.1, this section provides additional details of planned efficacy analyses. For time-to-event variables, the Kaplan-Meier method will be used to estimate parameters (for example, medians, quartiles, 6 months, and 1-year event rates). See also the SAP for additional details.

ORR: The denominator of ORR includes each evaluable patient. The numerator includes those patients counted in the denominator with a best overall tumor response of PR or CR.

DCR: Using the same denominator as for ORR, the numerator of the DCR includes those patients counted in the denominator with a best tumor response of SD, PR, or CR.

DOR: The DOR is defined only for responders (patients with a confirmed CR or PR, as defined in Section 10.1.1). It is measured from the date of first evidence of a confirmed CR or PR to the date of objective progression or the date of death due to any cause, whichever is earlier. If a responder is not known to have died or have objective progression as of the data inclusion cutoff date, DOR will be censored at the date of the last complete objective progression-free disease assessment.

PFS: The PFS time is measured from the date of first dose to the date of objective progression or the date of death due to any cause, whichever is earlier. The censoring is taken in the following order:

- if a patient does not have a complete baseline disease assessment, then the PFS time will be censored at the first dose date, regardless of whether or not objectively determined disease progression or death has been observed for the patient; otherwise,
- if a patient is not known to have died or have objective progression as of the data inclusion cutoff date for the analysis, the PFS time will be censored at the last complete objective progression-free disease assessment date.

OS: OS duration is measured from the date of first dose to the date of death from any cause. For each patient who is not known to have died as of the data-inclusion cutoff date for a particular analysis, OS will be censored for that analysis at the last known alive date. ORR, DCR, DOR, and PFS will be assessed based on RECIST 1.1.

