5.5.6.2. Progression-Free Survival (PFS)

Progression-free survival is defined as the time from the date of first dose of study drug until first observation of objective (radiographically documented) PD as defined by RECIST version 1.1 or death from any cause, whichever comes first. The censoring is taken in the following order

- If a patient does not have an adequate baseline radiological tumor assessment, then the PFS time will be censored at the date of first study drug, regardless of whether or not objectively determined disease progression or death has been observed for the patient; otherwise,
- If a patient is not known to have died or have objective progression as of the data inclusion cutoff date for the analysis, the PFS time will be censored at the last adequate objective progression-free disease assessment date.

Adequate radiological tumor assessment refers to an assessment with one of the following responses: CR, PR, SD or PD. If a tumor assessment was done on multiple days, the earliest date for that visit will be used if overall response is PD, and the last date will be used otherwise (censor).

Progression-free survival sensitivity analysis will be performed. The censoring rules for PFS sensitivity analysis are listed in [Table JFCQ.5.2](#).

Table JFCQ.5.2. Rules for Determining Date of Progression or Censor for PFS Sensitivity Analysis

Situation	Event / Censor	Date of Event or Censor
Tumor progression or death	Event	Earliest date of PD or death
No tumor progression and no death	Censored	Date of last adequate radiological assessment or date of first dose (whichever is later)
unless		
No baseline radiological tumor assessment available	Censored	Date of first dose
No adequate post baseline radiological tumor assessment available and death reported after 2 scan intervals following first dose	Censored	Date of first dose
New anticancer treatment started and no tumor progression or death within 14 days	Censored	Date of adequate radiological assessment prior to (start of new therapy +14 days) or date of first dose (whichever is later)
Tumor progression or death documented immediately after 2 or more scan intervals following last adequate radiological tumor assessment or first dose (whichever is later)	Censored	Date of last adequate radiological assessment or date of first dose (whichever is later)

Notes:

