- (1) Symptomatic deteriorations (i.e., symptomatic progressions, which are not radiologically confirmed) will not be considered as progressions
- (2) 2 scan intervals = 90 days# for this trial
#: 2*(6 weeks+5 days window)

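### Protocol 9.6 counts palliative radiotherapy as progression for PFS, against the PFS definitions; separately, the SAP's 90-day limit does not match its own formula, which gives 94

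*Protocol*

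**What the plan says.** **Radiotherapy.** Protocol 9.6 permits palliative radiotherapy on study unless PD is the reason for it. A bullet below that line covers radiation to a single symptomatic lesion or to the brain, which "may be considered on an exceptional case-by-case basis after consultation with the sponsor". The bullet ends: "Administration of palliative radiation therapy will be considered clinical progression for the purposes of determining PFS".

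The PFS definitions read differently:

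- Protocol synopsis, Criteria for Evaluation: PFS runs "until the date of radiographically documented PD or death due to any cause, whichever is earlier".
- Protocol 12.2.7: PFS is "measured from the date of first dose to the date of objective progression or the date of death due to any cause".
- SAP 5.5.6.2: PFS runs to the "first observation of objective (radiographically documented) PD as defined by RECIST version 1.1 or death from any cause".

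None of them lists radiotherapy or clinical progression as an event. Note 1 to SAP Table JFCQ.5.2 (the PFS sensitivity analysis) adds: "Symptomatic deteriorations (i.e., symptomatic progressions, which are not radiologically confirmed) will not be considered as progressions". A row of that table censors patients who start new anticancer treatment without progression or death within 14 days. SAP 5.7.3 lists radiotherapy as one type of postdiscontinuation anticancer therapy.

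**Two scan intervals.** Note 2 to the same table reads "2 scan intervals = 90 days# for this trial" and gives the derivation 2 × (6 weeks + 5-day window). Two rows use the limit. One censors, at first dose, a death after two intervals with no adequate post-baseline assessment. The other censors PD or death that follows two or more intervals after the last adequate assessment, or after first dose if that is later.

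**The concern.** On the first point, approved text gives more than one status for the same patient. Someone irradiated without radiographic PD is a PFS event under protocol 9.6 and not an event under SAP 5.5.6.2. If on-study radiation counts as new anticancer treatment, that patient is censored in the sensitivity analysis. The SAP never mentions the 9.6 rule, so a site or programmer could follow either text. Counting radiation as an event can only bring event times forward.

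The question of what counts as new anticancer treatment also reaches best response. Protocol 10.1.3.2 and SAP 5.5.5 exclude responses seen after new anticancer therapy begins, and neither says whether on-study palliative radiation is such therapy.

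On the second point, the day count is a censoring threshold. If it is too short, a progression found on an in-window scan after one missed scan is censored rather than counted. A death just past the limit with no post-baseline scan is sent back to the first-dose date.

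**Working it through.** **1. Radiotherapy.** The conflict shows when the passages are set side by side. Protocol 9.6 names a clinical event, and the three definitions require radiographic or objective PD, or death. The conflict stands on SAP 5.5.6.2 alone, without note 1.

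The documents give no radiotherapy rate and no expected median PFS, so the size can only be illustrated. Assumptions: 54 patients; exponential time to PD; PD seen at the first scan after it occurs (scans every 42 days ± 5); no other censoring; radiotherapy time uniform between first dose and observed PD. The estimated median is the 27th ordered time, over 20,000 simulated trials.

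| True median PFS (months) | Mean fall in estimated median, 1 irradiated patient | Mean fall, 3 irradiated patients (3/54 = 5.6%) |
|---|---|---|
| 3 | 0.05 | 0.14 |
| 4 | 0.06 | 0.17 |
| 6 | 0.09 | 0.26 |

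The fall in a typical (median) trial is 0 months with one such patient and 0.03 with three. For comparison, at a true median of 3 months the estimated median itself ranges from 2.8 to 5.4 months (central 95%).

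**2. Two scan intervals.** Inputs: interval 6 weeks = 42 days and window ±5 days (protocol 10.1.1 and 10.1.3.1.2); printed limit 90 days (note 2).

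- Printed formula: 2 × (42 + 5) = 94. The printed 90 is not reproduced.
- Other readings: 2 × 42 = 84; 2 × 42 + 5 = 89; 2 × (42 − 5) = 74; 3 × 30.4375 = 91.3. Only a 3-day window, 2 × (42 + 3), or a rounded 3 × 30 gives 90. Neither is the printed formula.
- Longest in-window gap across one missed scan: 84 + 5 + 5 = 94, which agrees with the formula.

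Share of single-missed-scan gaps censored: let the two scans fall a and b days from schedule, each uniform on the integers −5 to 5 (assumed). The gap is 84 + b − a. There are 11 × 11 = 121 equally likely pairs, of which 11 − d have b − a = d, for d from 0 to 10.

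| Rule | Pairs censored | Share |
|---|---|---|
| Gap > 90 | 4+3+2+1 = 10 | 8.3% |
| Gap ≥ 90 | 5+4+3+2+1 = 15 | 12.4% |
| Gap + 1 ≥ 90 (SAP 5.2 duration rule) | 6+5+4+3+2+1 = 21 | 17.4% |
| Gap ≥ 94 | 1 | 0.8% |
| Gap > 94 | 0 | 0% |

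If 5 of 54 patients had PD at such a scan (assumed), the 90-day limit would affect 5 × 10/121 = 0.4 to 5 × 21/121 = 0.9 patients.

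Death row: with exponential OS, P(death on days 91 to 94) = exp(−90L) − exp(−94L), where L = ln 2 / (median × 30.4375). For an assumed median OS of 6, 9 or 12 months this is 1.1%, 0.8% or 0.6%. With 3 patients lacking a post-baseline scan (assumed), that is 0.03, 0.02 or 0.02 patients.

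**The case against.** The strongest reply is that the main analysis is already settled. The SAP governs the derivation of PFS and requires radiographically documented PD, the synopsis and protocol 12.2.7 agree, and protocol 12.2.1 lets the SAP clarify analyses. On this view 9.6 holds one stray sentence that a programmer working from the SAP would never use. Most of this stands, and it is why the point is minor. It does not remove the contradiction from the current protocol. It also leaves open how the sensitivity analysis treats an irradiated patient.

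Two further replies limit how the first error may be argued. Note 1 belongs to the sensitivity table, speaks of symptomatic deterioration and does not name radiotherapy, so it is supporting text at most. The exceptional-basis wording in 9.6 applies to a single symptomatic lesion or the brain, while the line above it permits palliative radiotherapy more generally. It is therefore unclear how far the PFS sentence reaches, and the wording cannot be used to show that all such radiation would be rare.

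On the second error, it is fair to say that the documents do not prove which side of note 2 is the slip. A 3-day window would give 90, and 3 days is the treatment-cycle window in protocol 9.4, but that origin is only a guess. The boundary is arguable too: the missed-scan row combines an after with a two-or-more, and the death row says only after. Hence the range of 8% to 17% rather than a single figure.

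**Conclusion.** Both errors are in the current text, and both are minor. Protocol 9.6 sets a PFS event that the synopsis, protocol 12.2.7 and SAP 5.5.6.2 do not recognise. SAP note 2 prints 90 days where its own formula gives 94. PFS is a secondary Part B endpoint with no hypothesis test.

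The effect of the first is unknown and probably small: mean falls of 0.05 to 0.26 months in the estimated median under the assumptions above, well inside its sampling range. The second is confined to the PFS sensitivity analysis. It censors 8% to 17% of single-missed-scan gaps if timing is uniform within the windows, which is likely to mean less than one patient.

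A reader might infer three stronger things that the documents do not support:

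- **That main PFS is undefined.** It is clear if the SAP is followed.
- **That 94 is proven to be the intended limit.** The formula and the imaging window both favour it, but the sponsor's intention is not stated.
- **That the primary ORR result is compromised.** Neither error alters the ORR test or the sample size. What remains is a definition to settle: whether on-study palliative radiation counts as new anticancer therapy for the best-response cut-off.

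**What to change.** **Radiotherapy.** Reconcile the passages:

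- State in SAP 5.5.6.2 that palliative radiotherapy without radiographic PD is not a PFS event in the main analysis, in line with the existing definitions. Protocol 12.2.1 leaves room for this: "Minor changes or clarifications to any statistical analyses described in this protocol may be presented in the final statistical analysis plan".
- State whether on-study palliative radiotherapy counts as new anticancer treatment, both for the censoring row of Table JFCQ.5.2 and for the best-response cut-off in protocol 10.1.3.2 and SAP 5.5.5.
- Delete the PFS sentence from protocol 9.6 at the next amendment.

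This changes endpoint wording only, not whether radiotherapy is allowed.

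**Two scan intervals.** Replace 90 with 94 in note 2, or correct the formula if the sponsor can show that 90 was intended. State once, for both rows, whether the limit means more than or at least that many days. State also whether the gap is a plain date difference or follows the +1-day duration rule in SAP 5.2. If no in-window scan after a single missed scan is to be censored, the rule is more than 94 days by plain date difference.

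**Cost.** A few SAP sentences, one number in a footnote and one protocol sentence deleted by amendment. No new data are needed.

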9.6.1. Supportive Care

Palliative and supportive care for other disease-related symptoms and for toxicity associated with treatment will be offered to all patients on this trial. Supportive care measures may include but are not limited to antidiarrheal agents, antiemetic agents, opiate and nonopiate analgesic agents, appetite stimulants, and granulocyte and erythroid growth factors. Details of interventions, procedures, or blood products (for example, blood cells, platelets, or fresh frozen plasma transfusions) should be recorded on the eCRF. Please see Section 9.4.1.3 for specific information on the management of necitumumab-related hypersensitivity/IRRs, skin reactions, conjunctivitis, electrolyte abnormalities, pneumonia and sepsis, and serious thromboembolic events. Guidelines regarding the use of other specific supportive care agents are presented below.

9.6.2. Colony-Stimulating Factors and Erythropoiesis-Stimulating Agents

The use of colony-stimulating factors (CSFs) or erythropoiesis-stimulating agents (ESAs) are permitted during investigational therapy at the discretion of the investigator.

Because recommendations on the use of CSFs/ESAs are rapidly evolving, investigators should frequently refer to the local, national, or international standards (for example, European

Organisation for Research and Treatment of Cancer, European Society for Medical Oncology, National Comprehensive Cancer Network, American Society of Clinical Oncology, American Society of Hematology, and/or Centers for Medicare and Medicaid Services Web sites) for the latest guidelines.

9.6.3. Therapy for Diarrhea/Colitis

Patients should be carefully monitored for signs and symptoms of enterocolitis (such as diarrhea, abdominal pain, blood or mucus in stool, with or without fever) and of bowel perforation (such as peritoneal signs and ileus).

In the event of diarrhea, the following supportive measures are allowed: hydration, octreotide, and antidiarrheals.

All patients who experience diarrhea/colitis should be advised to drink liberal quantities of clear fluids. If sufficient oral fluid intake is not feasible, fluid and electrolytes should be substituted via I.V. infusion. For Grade 2 or higher diarrhea, consider gastrointestinal consultation and endoscopy to confirm or rule out colitis.

- For **Grade 2 diarrhea/colitis**, oral corticosteroids are recommended.
- For **Grade 3 or 4 diarrhea/colitis**, intravenous steroids followed by high dose oral steroids are recommended.
- When symptoms improve to Grade 1 or less, steroid taper should be started and continued over no less than 4 weeks.

If diarrhea is severe (requiring intravenous rehydration) and/or associated with fever or severe (Grade 3 or 4) neutropenia, broad-spectrum antibiotics must be prescribed. Patients with Grade ≥ 3 diarrhea or any diarrhea associated with Grade ≥ 3 nausea or vomiting **must be hospitalized** for intravenous hydration and correction of electrolyte imbalances. Events that require a patient to be hospitalized are considered SAEs (see Section 10.2.1.1).

Pembrolizumab shall be withheld for moderate (Grade 2) or severe (Grade 3) colitis, and permanently discontinued for life-threatening (Grade 4) colitis.

